10.4.2. Men

Men, regardless of their fertility status, must agree to either remain abstinent (if this is their preferred and usual lifestyle) or use condoms as well as 1 additional highly effective method of contraception (less than 1% failure rate) or effective method of contraception with nonpregnant women of childbearing potential partners for the duration of the study and until their plasma concentrations are below the level that could result in a relevant potential exposure to a possible fetus, predicted to be 140 days after the last dose.

Men with pregnant partners should use condoms during intercourse for the duration of the study and until the end of estimated relevant potential exposure to the fetus, predicted to be 140 days after the last dose.

Acceptable Methods of Contraception for Female Partners of Male Participants

Highly effective methods of contraception (less than 1% failure rate) comprise, but are not limited to

- combination oral contraceptives
- implanted contraceptives, or
- intrauterine devices.

Effective methods of contraception comprise but are not limited to diaphragms with spermicide or cervical sponges.

Men and their partners may choose to use a double-barrier method of contraception that must include use of a spermicide.

10.4.3. Collection of Pregnancy Information

Male participants with partners who become pregnant

The investigator will attempt to collect pregnancy information on any male participant's female partner who becomes pregnant while the male participant is in this study. This applies only to male participants who receive study intervention.

After obtaining the necessary signed informed consent from the pregnant female partner directly, the investigator will record pregnancy information on the appropriate form and submit it to the sponsor within 24 hours of learning of the partner's pregnancy.

The female partner will also be followed up to determine the outcome of the pregnancy. Information on the status of the mother and child will be forwarded to the sponsor. Generally, the follow-up will be no longer than 6 to 8 weeks following the estimated delivery date. Any termination of the pregnancy will be reported including fetal status (presence or absence of anomalies) and indication for the procedure.

Female participants who become pregnant

The investigator will collect pregnancy information on any female participant who becomes pregnant while participating in this study. The initial information will be recorded on the appropriate form and submitted to the sponsor within 24 hours of learning of a participant's pregnancy.

The participant will be followed up to determine the outcome of the pregnancy. The investigator will collect follow-up information on the participant and the neonate, and the information will be forwarded to the sponsor. Generally, follow-up will not be required for longer than 6 to 8 weeks beyond the estimated delivery date. Any termination of pregnancy will be reported, including fetal status (presence or absence of anomalies) or indication for the procedure.

While pregnancy itself is not considered to be an AE or SAE, any pregnancy complication or elective termination of a pregnancy for medical reasons will be reported as an AE or SAE.

A spontaneous abortion (occurring at <20 weeks gestational age) or still birth (occurring at >20 weeks gestational age) is always considered to be an SAE and will be reported as such.

Any poststudy pregnancy-related SAE considered reasonably related to the study intervention by the investigator will be reported to the sponsor as described in Section 8.3.4. While the investigator is not obligated to actively seek this information in former study participants, he or she may learn of an SAE through spontaneous reporting.

10.5. Appendix 5: Genetics

Sample collection information is found in Appendix 2, Section 10.2.

Genetic variation may impact a participant's response to study intervention, susceptibility to, and severity and progression of disease. Variable response to study intervention may be due to genetic determinants that impact drug absorption, distribution, metabolism, and excretion; mechanism of action of the drug; disease etiology; and/or molecular subtype of the disease being treated. Therefore, where local regulations and IRB/IEC allow, a blood sample will be collected for DNA analysis from consenting participants.

DNA samples may be used for research related to SARS-CoV-2 and related diseases. They may also be used to develop tests/assays including diagnostic tests related to LY3819253 or SARS-CoV-2. Genetic research may consist of the analysis of 1 or more candidate genes or the analysis of genetic markers throughout the genome as appropriate.

The samples may be analyzed as part of a multistudy assessment of genetic factors involved in the response to LY3819253 or study interventions of this class to understand study disease or related conditions.

The results of genetic analyses may be reported in the clinical study report or in a separate study summary.

The sponsor will store the DNA samples in a secure storage space with adequate measures to protect confidentiality.

The samples will be retained at a facility selected by the sponsor or its designee while research on SARS-CoV-2 continues, but no longer than 15 years or other period as per local requirements.

10.6. Appendix 6: Recommended Laboratory Testing for Hypersensitivity Events

Laboratory assessments should be performed if the participant experiences generalized urticaria or if anaphylaxis is suspected.

- Collect sample after the participant has been stabilized, and within 1 to 2 hours of the event; however, samples may be obtained as late as 12 hours after the event as analytes can remain altered for an extended period of time. Record the time at which the sample was collected.
- Obtain a follow-up sample after approximately 4 weeks.

Clinical Lab Tests for Hypersensitivity Events

Hypersensitivity Tests	Notes
LY3819253 anti-drug antibodies (immunogenicity/ADA)	Selected test may be obtained in the event of anaphylaxis or systemic allergic/hypersensitivity reactions. Assayed by Lilly-designated laboratory. Results will not be provided to the investigative sites.
LY3819253 concentrations (PK)	Assayed by Lilly-designated laboratory. Results will not be provided to the investigative sites.
Tryptase	Assayed by Lilly-designated laboratory. Results will not be provided to the investigative sites. Urine N-methylhistamine testing is performed in addition to tryptase testing. Collect the first void urine following the event. Collect a follow-up urine sample after approximately 4 weeks. Note: If a tryptase sample is obtained more than 2 hours after the event (that is, within 2 to 12 hours), or is not obtained because more than 12 hours have lapsed since the event, collect a urine sample for N-methylhistamine testing.
N-methylhistamine	Assayed by Lilly-designated laboratory. Results will not be provided to the investigative sites.
Drug-specific IgE	Will be performed if a validated assay is available. Assayed by Lilly-designated laboratory. Results will not be provided to the investigative sites.
Basophil activation test	Will be performed if a validated assay is available. Assayed by Lilly-designated laboratory. Results will not be provided to the investigative sites. NOTE: The basophil activation test is an in vitro cell based assay that only requires a serum sample. It is a surrogate assay for drug specific IgE, but is not specific for IgE.
Complement (C3, C3a, and C5a)	Assayed by Lilly-designated laboratory. Results will not be provided to the investigative sites.
Cytokine panel	Assayed by Lilly-designated laboratory. Results will not be provided to the investigative sites.

Abbreviations: IgE = immunoglobulin E; PK = pharmacokinetic.

10.7. Appendix 7: Abbreviations

Term	Definition
ADE	antibody-dependent enhancement
AE	adverse event
AUC	area under the curve
AUC(0-∞)	AUC(0-∞) area under the concentration versus time curve from zero to infinity
CFR	Code of Federal Regulations
complaint	A complaint is any written, electronic, or oral communication that alleges deficiencies related to the identity, quality, purity, durability, reliability, safety or effectiveness, or performance of a drug or drug delivery system.
Compliance	Adherence to all study-related, good clinical practice (GCP), and applicable regulatory requirements.
COVID-19	coronavirus disease-2019
CRF	case report form
CRP	clinical research physician: Individual responsible for the medical conduct of the study. Responsibilities of the CRP may be performed by a physician, clinical research scientist, global safety physician or other medical officer.
CRU	clinical research unit
ECG	electrocardiogram
eCRF	electronic case report form
EDC	electronic data capture
enroll	The act of assigning a participant to a treatment. Participants who are enrolled in the study are those who have been assigned to a treatment.
Enter	Participants entered into a study are those who sign the informed consent form directly or through their legally acceptable representatives.
FDA	United States Food and Drug Administration
FSH	follicle-stimulating hormone
GCP	good clinical practice
HCV	hepatitis C virus
HIV	human immunodeficiency virus

Term	Definition
IB	Investigator's Brochure
ICF	informed consent form
ICH	International Council for Harmonisation
IEC	independent ethics committee
Informed consent	A process by which a participant voluntarily confirms his or her willingness to participate in a particular study, after having been informed of all aspects of the study that are relevant to the participant's decision to participate. Informed consent is documented by means of a written, signed and dated informed consent form.
Investigational product	A pharmaceutical form of an active ingredient or placebo being tested or used as a reference in a clinical trial, including products already on the market when used or assembled (formulated or packaged) in a way different from the authorized form, or marketed products used for an unauthorized indication, or marketed products used to gain further information about the authorized form.
IRB	institutional review board
ISR	injection site reaction
IV	intravenous(ly)
mAb	monoclonal antibody
participant	Equivalent to CDISC term "subject": an individual who participates in a clinical trial, either as recipient of an investigational medicinal product or as a control
PK	pharmacokinetics
PYAA	J2W-MC-PYAA
PYAB	J2W-MC-PYAB
PYAG	J2X-MC-PYAG
SAE	serious adverse event
SAP	statistical analysis plan
SARS-CoV-2	severe acute respiratory syndrome coronavirus 2
SC	subcutaneous(ly)
screen	The act of determining if an individual meets minimum requirements to become part of a pool of potential candidates for participation in a clinical study.
SoA	Schedule of Activities

Term	Definition
TEAE	Treatment-emergent adverse event: An untoward medical occurrence that emerges during a defined treatment period, having been absent pretreatment, or worsens relative to the pretreatment state, and does not necessarily have to have a causal relationship with this treatment.
t_{max}	time of maximum observed drug concentration
VAS	visual analog scale

10.8. Appendix 8: Protocol Amendment History

Amendment (a)

Overall Rationale for the Amendment:

Following feedback from the U.S. Food and Drug Administration (FDA), typographical errors have been corrected. Additional changes described below have been made for clarity for clinical site activities.

Section # and Name	Description of Change	Brief Rationale
Section 1.3. Schedule of Activities	
Physical Examination/Medical Assessment
 
 Corrected “Visit 7/ED” to “Visit 6/ED” 
Injection Site Assessments
 
 Simplified language in Comments column to denote ISR assessment, pain VAS and Scarletred for all timepoints, and added clarification regarding predose Scarletred timing. 	
There is no Visit 7 per the Schedule of Activities. Typographical correction.
 
Scarletred will be assessed during the predose activities.

Section 5.2. Exclusion Criteria	Updated Criterion 12.a to correct for typo: “within 2 minutes” should be “within 2 meters .”	FDA feedback. Typographical correction.
Section 6.1. Study Interventions Administered	LY3819253 unit dose and strength updated to 262.5 mg/2.1 mL vial (125 mg/mL).	Clarification added for vial fill volume (2.1 mL) and drug product concentration (125mg/mL).
Section 6.1.1. Injection Volumes and Formulation Concentrations	Updated Cohort 3 injection volumes to reflect syringe accuracy specification: “3x 1.86 mL” updated to “2x 1.9 mL + 1x 1.8 mL.”	Due to limitations with syringe gradations, accurate measurement of 0.06 mL with a 3-cc syringe is not possible. Therefore, the injection volume was rounded to 1 decimal to enable accurate volume for dosing.
Section 10.7. Appendix 7, Abbreviations	Added FDA to list of abbreviations.	FDA used on this page.

11. References

<https://doi.org/10.1073/pnas.2004168117>.
- Gilead Sciences, Inc. Fact sheet for health care providers: emergency use authorization (EUA) of Veklury® (remdesivir). July 2020. Accessed August 13, 2020.
<https://www.fda.gov/media/137566/download>.

2. ABBREVIATIONS

Abbreviations pertain to the Statistical Analysis Plan (SAP) only (not the tables, figures and listings [TFLs]).

%AUC($t_{last-\infty}$)	Percentage of AUC(0- ∞) extrapolated
ADA	Antidrug antibody
AE	Adverse event
AUC	Area under the concentration versus time curve
AUC(0- ∞)	Area under the concentration versus time curve from time zero to infinity
AUC(0- t_{last})	Area under the concentration versus time curve from time zero to time t, where t is the last time point with a measurable concentration
BQL	Below the lower limit of quantitation
CL/F	Apparent total body clearance of drug calculated after extra-vascular administration
C_{max}	Maximum observed drug concentration
CRF	Case Report Form
CRU	Clinical Research Unit
CSR	Clinical Study Report
CV	Coefficient of variation
ECG	Electrocardiogram
ICH	International Conference on Harmonisation
ISR	Injection-site reaction
MedDRA	Medical Dictionary for Regulatory Activities
PK	Pharmacokinetic
SAE	Serious adverse event
SAP	Statistical Analysis Plan
SARS-COV-2	Severe acute respiratory syndrome coronavirus 2
SC	Subcutaneous
SD	Standard deviation
$t_{1/2}$	Half-life associated with the terminal rate constant (λ_z) in non-compartmental analysis
TE ADA	Treatment-emergent antidrug antibodies
TEAE	Treatment-emergent adverse event

TFLs	Tables, Figures, and Listings
t_{\max}	Time of maximum observed drug concentration
VAS	Visual analog scale
V_z/F	Apparent volume of distribution during the terminal phase after extra-vascular administration
WHO	World Health Organization

3. INTRODUCTION

This SAP has been developed after review of the Clinical Study Protocol (final version dated 17 August 2020).

This SAP describes the planned analysis of the safety, tolerability and pharmacokinetic (PK) data from this study. A detailed description of the planned TFLs to be presented in the clinical study report (CSR) is provided in the accompanying TFL shell document.

The intent of this document is to provide guidance for the statistical and PK analyses of data. In general, the analyses are based on information from the protocol, unless they have been modified by agreement with Eli Lilly and Company. A limited amount of information concerning this study (e.g., objectives, study design) is given to help the reader's interpretation. When the SAP and TFL shells are agreed upon and finalized, they will serve as the template for this study's CSR.

This SAP supersedes the statistical considerations identified in the protocol; where considerations are substantially different, they will be so identified. If additional analyses are required to supplement the planned analyses described in this SAP, they may be performed and will be identified in the CSR. Any substantial deviations from this SAP will be agreed upon with Eli Lilly and Company and identified in the CSR. Any minor deviations from the TFLs may not be documented in the CSR.

This SAP is written with consideration of the recommendations outlined in the International Conference on Harmonisation (ICH) E9 Guideline entitled Guidance for Industry: Statistical Principles for Clinical Trials¹ and the ICH E3 Guideline entitled Guidance for Industry: Structure and Content of Clinical Study Reports².

4. STUDY OBJECTIVES AND ENDPOINTS

[figure not shown]
Objectives	Endpoints
Primary To determine the PK of single subcutaneous (SC) doses of LY3819253 in healthy participants	Area under the concentration versus time curve from time zero to infinity (AUC(0-∞))
Secondary To describe safety and tolerability following single SC doses of LY3819253 in healthy participants	Incidence of spontaneously reported adverse events (AEs), treatment-emergent adverse events (TEAEs), and serious adverse events (SAEs); vital signs; clinical laboratory results
Exploratory To assess injection-site reactions (ISRs) following single SC doses of LY3819253 in healthy participants	Characterization and measurement of incidence and severity of ISRs, including injection site pain, using data collected from the ISR assessment, as well as the exploratory tool (Scarletred).

To determine the immunogenicity of LY3819253 following single SC doses in healthy participants.	Incidence of treatment-emergent antidrug antibodies (TE ADA).
---	---

5. STUDY DESIGN

5.1 Overall Design

This is a single-site study in healthy participants who will receive a single SC dose of LY3819253. The study will be participant- and investigator-blinded, randomized, and placebo controlled. A study schema for this study can be seen in [Figure 1](#).

Abbreviations: LY = LY3819253; PBO = placebo; SC = subcutaneous.

Figure 1: Study Schema for Study J2X-MC-PYAG

5.2 Screening and Enrollment

Up to 3 cohorts may be enrolled with at least 9 participants per cohort (7 LY3819253: 2 placebo), with the intention that at least 6 participants randomized to LY3819253 have sufficient evaluable data in each cohort.

Participants will be screened within 14 days prior to Day 1 of dosing for each cohort. Participants will be admitted to the clinical research unit (CRU) as part of an inpatient visit on Day -1 and will be sequentially enrolled and then randomized to treatment.

5.3 Inpatient Stay

Participants will be admitted to the study site on Day -1. They will remain inpatient until discharge on Day 7 after study procedures are complete.

Dosing

Dosing will occur on Day 1. Intended doses of LY3819253 are as follows:

- Cohort 1: 350 mg
- Cohort 2: 700 mg
- Cohort 3 (optional): 700 mg (alternative injection volumes)

Participants will undergo PK sampling and safety assessment after dosing.

For Cohorts 1 and 2, a safety review will be conducted to determine whether it is appropriate to proceed with dosing of the next cohort. This safety review will be conducted based on data from at least 4 participants, after at least 4 days after dosing.

Sentinel dosing

Cohort 1 will include sentinel dosing. The first 2 participants will be randomized and dosed (1 LY3819253: 1 placebo).

The investigator and the Lilly sponsor team are responsible for determining if safety and tolerability is acceptable to continue with dosing subsequent participants.

Tolerability as measured by ISRs and their severity is anticipated to be the main safety consideration for this assessment. While no serious systemic reactions have been seen with LY3819253 to date, participants will be closely monitored.

If the investigator and Lilly sponsor team determine that safety and tolerability is acceptable, the remaining participants in the cohort will be dosed on the next day.

Cohort 2 and the optional Cohort 3 will not include sentinel dosing.

Postdose sampling

On Days 1 through 7, participants will undergo PK sampling and safety assessment.

5.4 Outpatient Follow-up

Follow-up visits will be conducted through Day 85.

In the event a participant has suspected or confirmed severe acute respiratory syndrome coronavirus 2 (SARS-CoV-2) infection, follow-up visits may be conducted at the participant's home.

6. TREATMENTS

The following is a list of the study treatment abbreviations that will be used in the TFLs.

Cohort	Study Treatment Name*	Treatment order in TFL
All	Placebo SC	1
1	350 mg LY3819253 SC (2x 1.4 mL)	2
2	700 mg LY3819253 SC (1x 1.4 mL + 2x 2.1 mL)	3
3 (optional)	700 mg LY3819253 SC (1x1.8 mL + 2x 1.9 mL)	4

*The LY3819253 formulation concentration will be 125 mg/mL in all cases.

7. SAMPLE SIZE JUSTIFICATION

A maximum of 36 participants will be enrolled to study intervention with the intention that at least 6 participants randomized to LY3819253 have sufficient evaluable data in each cohort.

This would mean at least 12 participants with evaluable data if Cohorts 1 and 2 only are enrolled, or 18 participants if the optional Cohort 3 is also enrolled.

The sample size is not powered on the basis of statistical hypothesis testing. However, based on an assumption of 40% coefficient of variation (CV) for between subject variability in a PK parameter of interest, 6 subjects on active treatment per cohort may provide approximately 70% chance to ensure that a PK parameter's 90% confidence interval (CI) falls within (0.7, 1.43) over the corresponding geometric mean, such as AUC(0-∞).

A participant will be considered evaluable when the participant completes up to 29 days of study procedures. When a participant does not complete up to 29 days of study procedures, the sponsor will be consulted if the participant will need to be replaced.

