4.1.1. Screening and enrollment

Up to 3 cohorts may be enrolled. In Cohorts 1 and 2, there will be at least 9 participants per cohort (7 LY3819253:2 placebo), with the intention that at least 6 participants randomized to LY3819253 have sufficient evaluable data in each cohort.

For the optional Cohort 3, up to 9 participants will be enrolled and the cohort may be closed when at least 5 participants have been randomized to LY3819253. The number of participants and the ratio of LY3819253 to placebo may change based on enrollment numbers. However, the number assigned to LY3819253 will not exceed 7, and the number assigned to placebo will not exceed 2.

Participants will be screened within 14 days prior to Day 1 of dosing for each cohort. Participants will be admitted to the CRU as part of an inpatient visit on Day -1 and will be sequentially enrolled and then randomized to treatment.

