9.2. Sample Size Determination

A maximum of 36 participants will be enrolled to study intervention with the intention that at least 6 participants randomized to LY3819253 have sufficient evaluable data in each of Cohorts 1 and 2.

This would mean at least 12 participants with evaluable data if Cohorts 1 and 2 only are enrolled. If the optional Cohort 3 is used, the total number of participants in the study with evaluable data will depend on enrollment numbers for that cohort.

The sample size is not powered on the basis of statistical hypothesis testing. However, based on an assumption of 40% CV for between subject variability in a PK parameter of interest, 6 subjects on active treatment per cohort may provide approximately 70% chance to ensure that a PK parameter's 90% confidence interval falls within (0.7, 1.43) over the corresponding geometric mean, such as AUC(0-∞).

A participant will be considered evaluable when the participant completes up to 29 days of study procedures. When a participant does not complete up to 29 days of study procedures, the sponsor will be consulted if the participant will need to be replaced.

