11. CHANGES FROM THE PROTOCOL SPECIFIED STATISTICAL ANALYSES

There were no changes from the protocol specified statistical analyses.

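### SAP 5.2 and 7 apply minimum numbers and a roughly 70% precision statement to every cohort, but the current protocol limits the minimums to Cohorts 1 and 2, so neither is assured for the optional Cohort 3

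*SAP*

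**What the plan says.** **Enrolment.** SAP 5.2: "Up to 3 cohorts may be enrolled with at least 9 participants per cohort (7 LY3819253: 2 placebo", with no exception for Cohort 3. Protocol 4.1.1 gives the 9-participant minimum (7 LY3819253, 2 placebo) for Cohorts 1 and 2 only. For Cohort 3 it states that "up to 9 participants will be enrolled and the cohort may be closed when at least 5 participants have been randomized to LY3819253", with at most 7 on LY3819253 and 2 on placebo.

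**Evaluable numbers.** SAP 7 intends at least 6 evaluable on LY3819253 in each cohort, hence 12 with two cohorts, "or 18 participants if the optional Cohort 3 is also enrolled". Protocol 9.2 restricts that intention to Cohorts 1 and 2. If Cohort 3 is used, it says that "the total number of participants in the study with evaluable data will depend on enrollment numbers for that cohort".

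**Precision.** SAP 7 takes a between-subject CV of 40%. Its claim is worded per cohort: "6 subjects on active treatment per cohort may provide approximately 70% chance to ensure". The target is a 90% CI inside (0.7, 1.43) relative to the geometric mean. Protocol 9.2 carries the same statement.

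**Status of the SAP.** SAP 3 says it was written from the protocol dated 17 August 2020, and adds: "This SAP supersedes the statistical considerations identified in the protocol". Substantial differences are to be identified. SAP 11 then reports: "There were no changes from the protocol specified statistical analyses".

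**The concern.** For Cohort 3, the SAP's minimum of 9 enrolled is the protocol's maximum. The SAP also keeps an evaluable target and a total that the protocol does not set once Cohort 3 is used. Both texts are current, so the conflict does not depend on the amendment history.

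Cohort 3 is the only planned cohort that gives 700 mg in the alternative injection volumes. A reader of the SAP would expect 6 evaluable there and about a 70% chance of the stated precision for AUC(0-∞). The protocol allows the cohort to close with fewer, and the 5 are counted at randomization, not as evaluable. SAP 3 makes the SAP and its table shells the template for the study report, so the figures could carry over into it.

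**Working it through.** **Inputs**
- Between-subject CV 40% (SAP 7). The log-scale SD σ is √ln(1 + 0.4²) = √ln 1.16 = 0.385, or 0.40 if the CV is used directly. The SAP does not say which, so both are shown.
- Limits 0.7 and 1.43 (SAP 7): −ln 0.7 = 0.3567 and ln 1.43 = 0.3577. The narrower, H = 0.3567, is used below.
- Two-sided 90% CI (SAP 9.3.2), so the 0.95 quantile of t.
- n = 6 per cohort (SAP 7). For Cohort 3, n = 5 is the lowest closing number and n = 7 the cap (Protocol 4.1.1). n = 4 represents one non-evaluable participant out of 5.

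**Formula.** The CI half-width on the log scale is t·s/√n. It stays within H when s ≤ H√n/t. With ν degrees of freedom for s,

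P = Pr[χ²(ν) ≤ ν·(H√n / (t·σ))²].

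**Step 1: reproduce the stated figure.** With the cohort's own SD, ν = n − 1. At n = 6, t = 2.015 and the largest admissible s is 0.3567 × √6 / 2.015 = 0.434.
- σ = 0.385: χ² limit 5 × (0.4336/0.3853)² = 6.33, P = 72.5%.
- σ = 0.40: χ² limit 5 × (0.4336/0.40)² = 5.88, P = 68.1%.

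Using ln 1.43 instead gives 72.8% and 68.5%. The stated figure therefore reproduces at 68% to 73%, and its basis is the cohort's own SD.

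**Step 2: the same calculation at the sizes allowed for Cohort 3**

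| n evaluable | t | P, σ = 0.40 | P, σ = 0.385 |
|---|---|---|---|
| 4 | 2.353 | 36.8% | 39.7% |
| 5 | 2.132 | 52.2% | 56.2% |
| 6 | 2.015 | 68.1% | 72.5% |
| 7 | 1.943 | 81.8% | 85.4% |

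Closing at 5, all evaluable, costs about 16 percentage points against n = 6.

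**Step 3: the planned model.** SAP 9.3.2 fits an ANOVA to ln AUC(0-∞) with dose as a factor, so its CIs use a pooled residual variance. Taking the three cohorts as three groups (an assumption, because two share the 700 mg dose), ν = total − 3. Precision for Cohort 3:

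| Evaluable, Cohorts 1, 2, 3 | ν | P, σ = 0.40 | P, σ = 0.385 |
|---|---|---|---|
| 6, 6, 6 | 15 | 92.2% | 95.1% |
| 6, 6, 5 | 14 | 79.1% | 84.8% |
| 6, 6, 4 | 13 | 56.6% | 64.1% |

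**Step 4: the total.** The SAP's 18 is 3 × 6. With Cohorts 1 and 2 at their intended minimum and Cohort 3 closed at 5, it is 6 + 6 + 5 = 17, or fewer if any of the 5 is not evaluable. If Cohorts 1 and 2 keep their planned 7 each, it is 7 + 7 + 5 = 19.

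**The case against.** Several arguments limit this point, and most of them stand.

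- **Nothing is guaranteed.** The 6 evaluable is an intention, and the 70% statement is hedged and conditional on n = 6. Only the minimum of 9 in SAP 5.2 is worded firmly.
- **Closure at 5 is permitted, not planned.** Up to 7 may receive LY3819253 in Cohort 3, and 6 or 7 evaluable would meet the stated figure. A reader might infer that Cohort 3 will miss its size and precision; the documents support only that these are not assured.
- **The own-SD figures are not those of the planned model.** With pooled variance and cohorts of 6, 6 and 5, the chance at n = 5 is above 70%. This is a fair limit on the consequence. But SAP 7's figure matches the own-SD calculation, so 52% to 56% is the like-for-like comparison. Pooling does not remove the loss either: it is about 10 to 13 points from 6, 6, 6 to 6, 6, 5, and with only 4 evaluable the pooled figure is below 70%.
- **The SAP does not override the protocol's enrolment rule.** A reader might infer from SAP 3 that SAP 5.2 governs enrolment. But SAP 3 gives precedence over statistical considerations only, and describes study design information as an aid to interpretation. The argument reaches SAP 7, not SAP 5.2.
- **No result depends on 6 or 18.** No hypothesis test is planned, the PK population takes every treated participant with sufficient samples, and the report will show the actual N and CIs. The outlier procedure in SAP 9.3.1 switches at n = 6, but on the actual number of values. This keeps the matter modest without making the two texts agree.

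**Conclusion.** The point holds as an inconsistency between current texts. SAP 5.2 and 7 state a size and apply a precision figure to every cohort; Protocol 4.1.1 and 9.2 do not assure that size for Cohort 3. SAP 7's own arithmetic is sound: 3 × 6 is 18, and about 70% at n = 6 reproduces.

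For Cohort 3 at n = 5 the chance is about 52% to 56% on the SAP's own-SD basis, and about 79% to 85% under the pooled ANOVA. These rest on a 40% CV, log-normal data, and, for the pooled figures, three groups with 6 evaluable in each of the other two. A total of 17 or fewer also requires Cohorts 1 and 2 to fall from their planned 7 each; closure of Cohort 3 at 5 alone does not bring the total below 18.

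A reader might also infer that the no-changes statement in SAP 11 is false. It concerns statistical analyses, and no analysis method differs here. Nor can the lag of the SAP be established: it cites the protocol of 17 August 2020, and the supplied text does not show the date of the current version. It should be corrected, but no planned analysis is invalidated.

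**What to change.** 1. SAP 5.2: restate enrolment as in Protocol 4.1.1, with the minimum of 9 for Cohorts 1 and 2 only, and the Cohort 3 ceiling and closing rule as the protocol has them.
2. SAP 7: limit the intention of 6 evaluable to Cohorts 1 and 2, delete the total of 18, and state, as Protocol 9.2 does, that the total depends on Cohort 3 enrolment.
3. SAP 7: limit the approximately 70% statement to Cohorts 1 and 2. For Cohort 3, give a range for n = 5 to 7 with the variance basis named: about 52% to 56% at n = 5 and 82% to 85% at n = 7 on the cohort's own SD. If the pooled figure is added, state the assumed sizes of the other cohorts.
4. SAP 3: confirm or update the protocol version cited.

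SAP 11 needs no change on this point once the texts agree. The cost is SAP wording and a less favourable precision figure for the optional cohort if it closes at 5. No participants are added and no analysis changes.
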